3.2. Sampling Strategy for Site Recruitment

The aim of the sampling strategy will be to recruit sites and site investigators that reflect routine treatment practice in their respective countries.

A master list of potential sites will be prepared for each country, based on practice information known to ARW and its local fieldwork partners, and with additional input as required from GSK local operating companies. Sites will be stratified by geographic region and, in addition, according to resident population densities within those regions.

Sites will be sampled such that good geographical representation is achieved within each country and that the number of site investigators recruited is proportionate to the treated patient population served in each geographical region. Thus, a region with twice the estimated patient population of another will be anticipated to provide a greater number of sites and/or site investigators.

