4. STUDY DESIGN

The study is a non-interventional, retrospective chart review of patients prescribed fondaparinux to treat their SVT. The study will be conducted in several EU countries. Qualified medical record abstractors will be identified at each site and specifically trained on the data collection required for the study.

It is essential that the study design and objective does not influence physician practice for treating those patients being included in the study. Consequently, the study will not begin recruitment until at least six months following availability and reimbursement of the product at the particular site. This delay should be sufficient to allow fondaparinux to be adopted into routine practice at each recruited site and to be prescribed to a sufficient number of patients per physician. Sites may be identified during this time period, however, recruitment will only begin after the six months have passed and a sufficient number of patients have accrued.

The site abstractor(s) will complete a short paper-based case report form (CRF) on the first consecutive 'n' SVT patients prescribed with fondaparinux by each physician practising at the site starting one month after the availability and reimbursement of fondaparinux, and who meet the other study inclusion criteria It is assumed that each site will have more than one physician who can provide patients for inclusion in the study. Thus, it is envisaged that one

physician will take the role of the site lead investigator, who would be the main point of contact during the study and would be responsible for coordinating site activities (e.g. assisting with EC submissions, data collection, etc.).

The lead investigator of each site will be fully briefed on the study objectives, methodology and data requirements prior to data collection.

Sites will track abstracted records by an identification log kept at the site to ensure that records can be re-accessed in the case of an outstanding query or audit. This information will not be entered into the database or retained by the sponsor. Consecutive records which fulfil the inclusion criteria are desired; however, if it is not possible to identify the date and dose of fondaparinux prescribed to eligible SVT patients in the source records, then these patient(s) may be excluded from the study.

The exclusion of any consecutive records will also be tracked.

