5. SAMPLE SIZE AND POWER/PRECISION CALCULATIONS

5.1. Sample Size Calculations

As the primary objective of the study is to obtain an estimate of physician adherence to the fondaparinux prescribing information for SVT, overall and per country, a methodology that takes into consideration the study design, i.e. patients nested within each physician and within each site, has been identified. This explicitly recognises the fact that the prescribing for different patients consulting the same physician is unlikely to be independent and will be correlated (the amount of correlation represented by the intra-class correlation coefficient). It is assumed that prescribing for patients consulting different physicians and sites is independent.

For any given total patient sample size, the higher the ratio of the number of participant physicians to the number of patients each physician recruits, the greater the power achieved. The design of the study intends to allow sites some flexibility (in order to ensure site participation) in the number of physicians and number of patients each may recruit. This flexibility is described in Table 2 below with minimum and target numbers defined. Upper limits in terms of the maximum permissible number of patients per physician and the maximum permissible number of physicians per site are also stated.

Table 2: Enrolment - Minimum, Target and Upper Limits Defined

		Enrolment	
	Target	Minimum	Upper limit
Physicians per country	30*	19	30*
Patients per physician	7	7	10
Patients per country	210*	133	210*
Physicians per site	2	1	5
Patients per site	14	7	20
Sites per country	15*	10	15*
Countries	4	4	4
Total No. Patients	840	532	840

^{*} Average across all countries

The patient sample calculations were based on using the technique described by Emrich and Piedmonte [6] contained within the R statistical package "mvtBinaryEP" [7]. Correlated binary data for a specific user-entered intraclass correlation coefficient could be generated.

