Monte Carlo simulations generating such correlated binary data (of the specified intra-class correlation, of the specified sample size, N, and assuming an underlying population probability of adherence of 0.8) were performed. For each simulated data set a Generalised Estimating Equation, GEE, containing a constant term was applied and the 95% confidence interval around the computed average percent adherence prediction was calculated. An indicator variable was created for each simulated data set which took the value 1 if the lower 95% confidence interval just described was above 60% and took the value 0 otherwise. The mean value of this indicator variable was then calculated across all simulation runs and represents the power of achieving a lower bound greater than 60% (given an assumed adherence rate of 80% and a specified intra-class correlation) from the stated sample size/mix.

Table 3 below demonstrates how the power can vary for the same patient sample size of 210 by varying the intra-class correlation and/or the mix of number of physicians and patients managed per physician. The higher the intra-class coefficient the greater the benefit from increasing the number of physicians selected and decreasing the number of patients managed per physician to generate the same total patient base. With this in mind it has also been decided that no one physician should provide more than ten patients to the study (see appendix 9.4).

Table 3: Power Calculations for Minimum and Target Physician Numbers with varying intra-class correlations

	Intra-class correlation	Power
Scenario 1 (210 patients)	0.1	0.998
30 physicians, 7 patients each	0.2	0.974
total 210 patients	0.25	0.963
	0.3	0.937
Scenario 2 (210 patients)	0.1	0.994
21 physicians, 10 patients each	0.2	0.950
total 210 patients	0.25	0.916
	0.3	0.874
Scenario 3 (180 patients)	0.1	0.981
18 physicians, 10 patients each	0.2	0.900
total 180 patients	0.25	0.854
	0.3	0.807
Scenario 4 (Minimum sample)	0.1	0.964
19 physicians, 7 patients each	0.2	0.891

0.804

total 133 patients	0.25	0.846

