8b.	In those patients for whom imaging is performed, would the details and results of diagnostic imaging be	□ Yes, imaging details□ Yes, imaging results□ No

9.	Following diagnosis, after what period of time would you normally follow up with an SVT patient?	 □ days	or	□ weeks
	routinely recorded in the patient's record?			

Thank you! Would you be interested in taking part in an observational, non-interventional study looking at the treatment of patients with SVT? The study will require each participating site to provide simple information on up to 14 patients meeting certain criteria from a representative sample of physicians within your practice setting.

If you are interested in the study, we will contact you again shortly with further information.

If 'Yes', please record full contact de	tails:
Name:	
Institution:	
Address:	Address:
	
	Telephone:
	
City:	Facsimilie:
_	_

If 'No': Can I please ask why you do not want to participate?

[INTERVIEWER: ALL ANSWERS SHOULD BE SPONTANEOUS. DO NOT READ OUT LIST BELOW]

TOO BUSY STUDY DOES NOT INTEREST DOCTOR ETHICAL CONCERNS ETHICAL RESTRICTIONS FROM PRACTICE/HOSPITAL DOES NOT WANT TO INVOLVE OWN PATIENTS	1 2 3 4 5	
OTHER [RESPONSE TO Q3b - REFERRED TO ANOTHER SETTING	7 6]	THANK AND CLOSE

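### Table 2 cannot accommodate every physician at a site with three or more qualifying prescribers, and no rule says which ones contribute, so non-random choice is permitted

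*Supplement*

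**What the plan says.** Section 3.2 sets the goal: "The aim of the sampling strategy will be to recruit sites and site investigators that reflect routine treatment practice in their respective countries". Section 4.1 selects sites at random within geographical strata.

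Within a site, Section 4 has the abstractor complete a form for a consecutive run of eligible fondaparinux patients of every physician working there. The run starts one month after the product is available and reimbursed. Its length is written only as n, and excluded records are tracked.

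Table 2 in Section 5.1 gives these limits, in the order target, minimum, upper limit:
- "Physicians per site 2 1 5"
- "Patients per physician 7 7 10"
- "Patients per site 14 7 20"

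The same section explains, for both physicians and their patients: "The design of the study intends to allow sites some flexibility (in order to ensure site participation) in the number of physicians and number of"... The Site Assessment Survey (second Appendix 9.1) tells sites to expect to supply "up to 14 patients meeting certain criteria from a representative sample of physicians within your practice setting".

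On knowledge of the objective, the survey (Section 4.1) and the feasibility questionnaire (Section 4.2) withhold it. Later, Section 4 says: "The lead investigator of each site will be fully briefed on the study objectives, methodology and data requirements prior to data collection". Section 4.4 adds that the lead investigator receives the protocol and case report form before data collection starts.

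**The concern.** The study estimates physicians' adherence, and Section 5.1 assumes that one physician's prescribing decisions are correlated. Which physicians contribute is therefore a main determinant of the estimate. The rule in Section 4 would leave no choice, since everyone is included. Table 2 makes that rule unworkable at larger sites, so some physicians must be left out. The protocol does not say who decides, how, or when.

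If the choice leaned towards physicians thought to follow the prescribing information, the primary estimate would be too high and the sample would no longer reflect routine practice. The log of excluded records would not reveal it, because it covers skipped patients and not physicians who were never put forward. No planned analysis would reveal it either. The estimate answers a commitment made as part of EU approval, so an upward bias matters.

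**Working it through.** **1. The plan's own figure.** Table 3 gives the chance that the lower 95% limit for adherence exceeds 60%, "assuming an underlying population probability of adherence of 0.8". It was recomputed with 40,000 simulated data sets per cell, an intercept-only GEE with robust standard error, and limits on the logit scale.
- 30 physicians x 7, intra-class correlation (ICC) 0.2: 0.985, stated 0.974.
- 19 physicians x 7, ICC 0.2: 0.905, stated 0.891.
- 14 of the 16 cells agree within 2 points. The other two are slightly over 2 points high (18 x 10 at ICC 0.25: 0.876 against 0.854; 19 x 7 at ICC 0.3: 0.825 against 0.804).

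Table 3 is essentially reproduced. It treats the physicians as a random draw.

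**2. The Table 2 limits.** With 7 or more patients per physician and 20 or fewer per site:
- 2 x 7 = 14 and 2 x 10 = 20 both fit.
- 3 x 7 = 21 does not fit, and 5 x 7 = 35 is far over.

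The most that can contribute is two physicians, not five. Under the survey's ceiling of 14, it is exactly two at 7 each.

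**3. Possible size of the bias.** From the plan: adherence p = 0.80 and ICC 0.2. Assumed, because the documents give neither: k qualifying prescribers per site (3 to 5), and a correlation r between how adherent a physician seems to whoever chooses and that physician's true rate (0.3 or 0.5).

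The SD of physician rates is sqrt(p(1 - p) x ICC) = sqrt(0.8 x 0.2 x 0.2) = 0.179. Bias is approximately r x SD x m, where m is the mean of the top two of k standard normal values: 0.423, 0.663 and 0.829 for k = 3, 4 and 5. For k = 3 and r = 0.3 this is 0.3 x 0.179 x 0.423 = 0.023. Physician rates cannot exceed 1, so the size was also simulated with beta-distributed rates (200,000 sites per scenario):

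| k | r = 0.3, formula | r = 0.3, simulated | r = 0.5, formula | r = 0.5, simulated |
|---|---|---|---|---|
| 2 | 0 | 0 | 0 | 0 |
| 3 | 2.3 | 2.4 | 3.8 | 4.0 |
| 4 | 3.6 | 3.5 | 5.9 | 5.8 |
| 5 | 4.5 | 4.3 | 7.4 | 6.8 |

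(Percentage points of overstatement, two physicians picked at every site.)

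At ICC 0.3 and r = 0.3 the simulated range is 2.9 to 5.2 points. At ICC 0.1 the SD is sqrt(0.016) = 0.126, and the formula gives 0.3 x 0.126 x 0.423 = 1.6 points up to 0.3 x 0.126 x 0.829 = 3.1 points. If only a fraction f of sites has a choice, multiply by f. With half the sites, 2.4 to 6.8 becomes 1.2 to 3.4.

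The extreme case, every site supplying the best two as seen in the charts, gives expected estimates of 0.90 to 0.96 at ICC 0.2. With 7 of 15 sites doing so it gives 0.845 to 0.875. These are outer bounds, not expectations.

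**4. Choice of n.** Stopping each physician's series at its most favourable point between 7 and 10 moves the patient-weighted estimate from 0.80 to 0.818 to 0.828 (ICC 0.3 to 0.1). Taking 10 from physicians above the median rate and 7 from the rest gives 0.817 to 0.828 (ICC 0.1 to 0.3). Either way it is about 2 to 3 points at worst.

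**5. Timing.** The survey and feasibility stages are masked, and the briefing is not. No section places the choice of physicians, or of n, before or after the briefing.

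**The case against.** The protocol has real safeguards. The Protocol Summary says potential investigators are identified at random. Section 4 specifies consecutive patients, a fixed start and tracked exclusions. Section 7.7 gives physician recruitment to the vendor, and Section 7.5 lets the advisory committee advise on physician selection. The flexibility sentence is about how many physicians, not which. Feasibility charts are to be representative of each physician's patients, and the form records only whether data items are present.

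A reader might infer that lead investigators or site staff pick physicians after learning the objective. The documents do not support that: no section says who picks, and none places the choice after the briefing. The briefing and the protocol go to the lead investigator; the abstractors are described only as trained on data collection.

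Many sites may have no choice to make. Section 3.1 admits sites from 2 patients a month. Over the five months between the start of the patient series and the earliest recruitment, such a site would see about 2 x 5 = 10 patients, fewer if not all receive fondaparinux. At most one physician would then reach 7. The mix of larger sites is not given.

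This limits the size and likelihood of the bias, but it does not remove the conflict. None of the safeguards says which physicians contribute when three or more qualify. Nor can the 7-patient minimum be read as an average: Table 2's asterisk for averages is on the per-country rows only.

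**Conclusion.** The concern holds as a contradiction with a consequence. The instruction to include every physician cannot be met within Table 2 at a site with three or more qualifying prescribers, and nothing replaces it. The plan therefore permits non-random choice of physicians and does not require it to be made before the briefing. It does not show that such choice occurs.

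If it did, the overstatement would be about 2 to 7 points at ICC 0.2, assuming r of 0.3 to 0.5, three to five qualifying prescribers and selection at every site. It shrinks in proportion to the share of sites with a choice, and is zero where two or fewer qualify. The open n is secondary. This is more than a missing detail, because the stated limits defeat the stated sampling rule, and the remedy is cheap.

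**What to change.** Reconcile Section 4, Table 2 and the survey wording, including the limits of 5 physicians and 20 patients per site and the survey's ceiling of 14. Then specify:

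1. At the masked feasibility stage, before the protocol and case report form are released, each site gives the vendor a list of its physicians who prescribe for SVT, with counts of eligible patients. The survey already asks how many there are (question 5a).
2. The vendor takes all qualifying physicians if there are two or fewer, and otherwise draws two at random.
3. The number is fixed at the existing target of 7 consecutive patients per physician.
4. A drawn physician who declines or has too few records is replaced by the next in random order, with the reason logged.
5. The report gives eligible and participating physicians for each site.

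The target sample is unchanged: 15 sites x 2 physicians x 7 patients = 210 per country. If some of the 15 sites have only one qualifying physician, the count stays at the minimum of 19 or above with up to 11 such sites (30 - 11 = 19). The cost is a few protocol sentences, one list per site and a draw. Sites lose a little flexibility, which Section 5.1 values for participation, and there will be some replacement draws or refusals. Refusals bring back some self-selection, which is why they should be logged and reported.

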5.2. Planned Analyses

All statistical analyses will be conducted in Statistical Analysis Software (SAS) v9.1 or later. The proportion of patients treated according to the prescribing information for fondaparinux (the adherence rate) will be estimated using generalized estimating equations (GEEs).

5.2.1. Primary Analyses

Adherence estimates with confidence intervals will be derived using generalised estimating equations (GEE) overall and for each country [8]. The GEE will explicitly take into account the nesting of patients, per physician, within a medical practice.

Adherence in the current study will be defined as performing CUS, or other diagnostic imaging procedure, in order to rule out concomitant DVT prior to patients commencing fondaparinux therapy and ensuring that the recommended dose of fondaparinux is prescribed.

A sensitivity analysis will be conducted incorporating the length of the thrombus and the distance of the thrombus from the sapheno-femoral junction into the primary endpoint if the data is available.

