4.2. Feasibility Study

A feasibility study will be conducted in those randomly selected eligible sites to determine the availability of select data components within the medical chart. The feasibility study will comprise a simple questionnaire which will contain the variables of interest as a check list. Physicians who could act as the lead investigator at each eligible site will be asked to review the medical charts of those SVT patients meeting the criteria for the study, to determine the variables/data of interest that are routinely available for each patient. The patient charts to be reviewed will be representative of those treated by each physician within each site. Additionally, the number of patient charts to be reviewed will be equivalent to the number of eligible patients a site may have available for the main study (within the upper limits set out in the main study protocol).

The variables of interest will include as follows:

- Age
- Gender
- Renal status
- Presence/absence of concomitant DVT
- Length of thrombus
- Distance from sapheno-femoral junction
- Diagnostic procedures performed (e.g. ultrasound or other objective tests)
- Prescribed fondaparinux dose and duration.

This questionnaire will not contain any indication with regards to the overall objective of the study.

Between 12 and 18 eligible sites, proportionate to the country's population and representative of the country's main geographical regions, successfully completing the feasibility study will be invited to progress to the main study.

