The power results achieved for the scenarios in Table 3 show that the minimum sample required to still achieve a power ≥0.8 can be achieved by recruiting 10 sites (9 sites with 2 physicians per site and 1 site with 1 physician) with each physician reporting on 7 patients, resulting in a total of 133 patients. It is therefore thought acceptable to implement the targeting scheme with lower limits imposed as detailed in Table 3 ('Minimum sample'). Analysing all four countries will increase the sample size to 840 (4x210; best case scenario) or to 532 (4x133; worst case scenario) and will clearly improve the power beyond that of a single country. Therefore the power for all four countries will exceed 0.8.

0.3

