9.5 Protocol Amendment

This 20th November 2012 version of the protocol had two main amendments incorporated:

a. The present status for fondaparinux as a treatment for SVT across Europe, depending on several factors such as reimbursement or local prescription practices, means that it has been only possible to identify four countries to deploy the described study. As a consequence, the scope of the study described in this protocol has been amended to focus on four countries instead of five. In order to maintain the same patient sample (840 patients in total), the protocol now describes the recruitment of an average of fifteen sites per country, with a higher number of physicians overall per country.

b. The study timeline in the present version of the protocol has been updated to reflect the additional time associated with defining and implementing the requested feasibility study, identifying and agreeing the final selection of countries.

The milestones in section 7.4 have been updated to reflect the remaining study timeline.

This latest version of the protocol amendment addresses the uncertainty on the specificity of renal information after completion of feasibility in Germany, Slovenia and Greece. This led to the inclusion of a row 'serum creatinine' in the feasibility CRF and also the extension of the first question in the patient history section to include severity of renal function.

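### Per-country GEE intervals will rest on about 10 to 15 practices with no small-sample correction planned; ordinary GEE intervals would cover about 90–92% at site level, not 95%

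*Supplement*

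**What the plan says.** Section 5.2.1 sets the primary analysis: "Adherence estimates with confidence intervals will be derived using generalised estimating equations (GEE) overall and for each country". It adds: "The GEE will explicitly take into account the nesting of patients, per physician, within a medical practice". Section 5.2.2 applies the same method to the secondary endpoints. Section 5.2 names the software. None of these sections names the GEE cluster level, the variance estimator, the reference distribution or a small-sample adjustment.

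Section 5.1 bases the sample size on simulated data to which "a Generalised Estimating Equation, GEE, containing a constant term was applied and the 95% confidence interval" was computed. Power is the chance that the lower limit lies above 60% when true adherence is 80%. The simulation rests on this premise: "It is assumed that prescribing for patients consulting different physicians and sites is independent". On that basis section 5.1 concludes that "the minimum sample required to still achieve a power ≥0.8 can be achieved by recruiting 10 sites", that is, 19 physicians with 7 patients each.

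The number of practices per country is small under every statement of it. The floor is "recruiting 10 sites (9 sites with 2 physicians per site and 1 site with 1 physician". Appendix 9.5 gives "the recruitment of an average of fifteen sites per country". Section 4.2 invites: "Between 12 and 18 eligible sites, proportionate to the country's population".

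**The concern.** The usual GEE sandwich variance is a large-sample estimator in the number of clusters, not of patients. With few clusters it is biased low and is itself variable, and a normal quantile ignores that variability. Both faults narrow the interval.

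If the practice is the top level of nesting, as section 5.2.1 suggests, a country has 10 to 15 clusters. That is few enough for the shortfall to matter. The main product of the study is an adherence estimate with an interval in each country, so intervals that are too narrow overstate what each country's data show. The enrolment floor of 10 sites was also accepted on power computed from such an interval, with physicians rather than practices as the independent units.

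**Working it through.** **Inputs from the documents.** True adherence 0.8; 95% interval; criterion lower limit above 60%; physician ICC 0.1 to 0.3; 7 patients per physician; 10 sites with 19 physicians (minimum) or 15 sites with 30 physicians (target).

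**Assumed, because the documents give no value.** Correlation between patients of different physicians at the same site: zero, half, or all of the physician ICC.

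**Interval.** For an intercept-only logit GEE with independence working correlation and clusters i of size n_i, N = Σn_i:
- p̂ = ΣY_i/N and r_i = Y_i − n_i p̂
- SE of logit p̂ = √(Σr_i²) / [N p̂(1−p̂)] (uncorrected)
- Kauermann-Carroll replaces r_i by r_i/√(1−h_i), and Mancl-DeRouen by r_i/(1−h_i), with h_i = n_i/N
- limits: logit p̂ ± q × SE, back-transformed

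**Step 1: the plan's own power.** Simulated with physicians as independent clusters (correlated binary data from a thresholded normal, 40,000 runs per cell):

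| Power at ICC 0.1 / 0.2 / 0.25 / 0.3 | 30 × 7 | 19 × 7 |
|---|---|---|
| Table 3 | 0.998 / 0.974 / 0.963 / 0.937 | 0.964 / 0.891 / 0.846 / 0.804 |
| Uncorrected, normal quantile | 0.998 / 0.985 / 0.973 / 0.957 | 0.973 / 0.908 / 0.866 / 0.825 |

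Over all 16 cells the largest gap is 0.022. Corrected sandwiches with a normal quantile fit at least as well: largest gap 0.017 for Kauermann-Carroll and 0.015 for Mancl-DeRouen. Table 3 is therefore reproduced, but it does not reveal which variance estimator was used.

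**Step 2: hand check of coverage.** With K equal clusters the uncorrected variance is on average (K−1)/K of the right value. Treating cluster means as roughly normal, coverage is P(|t on K−1 df| < 1.96 × √((K−1)/K)):
- K = 10: 1.96 × √0.9 = 1.859, coverage 0.904
- K = 15: 1.96 × √(14/15) = 1.893, coverage 0.921
- K = 19: 1.96 × √(18/19) = 1.908, coverage 0.928
- K = 30: 1.96 × √(29/30) = 1.927, coverage 0.936

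**Step 3: simulation, uncorrected sandwich with normal quantile, ICC 0.1 to 0.3.**

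| Cluster in the GEE | Coverage at true 0.8 | Lower limit > 60% at true 0.6 (nominal 2.5%) |
|---|---|---|
| 10 sites | 0.899–0.909 | 4.4–4.9% |
| 15 sites | 0.918–0.925 | 3.6–3.9% |
| 19 physicians, independent | 0.929–0.932 | 2.9–3.4% across both physician rows |
| 30 physicians, independent | 0.937–0.939 | as above |

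A separate set of 20,000 runs per setting put the last column at about 3.6–4.6% for site clusters.

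If physicians are the clusters but physicians at one site are correlated at half the physician ICC, coverage is about 0.88–0.90. Correcting the variance at the wrong level does not cure this. At 15 sites, ICC 0.3 and within-site ICC 0.15, Kauermann-Carroll with t covers 0.911 with physician clusters and 0.949 with site clusters.

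**Step 4: corrected interval.** Site clusters, Kauermann-Carroll, t on sites minus 1: coverage at 0.8 is 0.944–0.956 (10 sites) and 0.948–0.955 (15 sites). The lower limit exceeds 60% at a true 60% in 2.2–2.5% and 2.3–2.5% of runs. At true adherence 0.9 coverage is about 93–95%.

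The widening on the logit scale, for equal clusters, is √(K/(K−1)) × t/1.96:
- K = 10: 1.054 × 2.262/1.96 = 1.22
- K = 15: 1.035 × 2.145/1.96 = 1.13

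**Step 5: power with the corrected interval.**

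| Sample | No within-site correlation, ICC 0.1 / 0.2 / 0.3 | ICC 0.3, within-site 0.15 |
|---|---|---|
| 10 sites, 19 physicians | 0.919 / 0.807 / 0.696 | about 0.55 |
| 15 sites, 30 physicians | 0.994 / 0.969 / 0.917 | 0.802 |

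Part of the fall in the last column comes from the assumed correlation, not from the correction. At 15 sites and ICC 0.3 the uncorrected site-level interval itself falls from 0.954 to 0.871 once the within-site ICC is 0.15.

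**The case against.** The strongest reply is that the plan never prescribes the method that fails. A reader might infer from the close match to Table 3 that uncorrected sandwich intervals with a normal quantile are the chosen method. The documents do not support that: corrected sandwiches reproduce the table equally well, and the match concerns physician clusters in a power simulation, not the planned site-level analysis. This stands, so the loss of coverage must be stated conditionally.

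A second reply is that variance options and degrees of freedom are commonly left to an analysis plan, and none is shown. That carries weight against a bare complaint of omission. But the protocol has already used an interval of this kind to accept a 10-site floor, and the alternative proposed here is a better method for the primary output, not a request for more text.

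Third, under section 5.1's independence assumption the shortfall is only one to two percentage points. That also stands for that assumption. However, section 5.2.1 undertakes to allow for the practice level, so the analysis and the power calculation do not use the same structure.

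A reader might also treat 60% as a pass mark and the 3.6–4.6% as a false-positive rate for a declared test. Section 5.1 uses 60% only to define power, and section 5.2.1 sets no success rule.

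Finally, 10 sites is the floor and 15 an average, so many countries may lie nearer the milder end.

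**Conclusion.** The concern holds in conditional form. Every normal-quantile site-level setting examined under-covers. With the uncorrected sandwich, coverage at true adherence 0.8 is about 90–91% with 10 sites and 92% with 15. It is about 93–94% with 19 to 30 truly independent physicians, and about 88–90% if physicians are the clusters while same-site physicians are correlated at half the physician ICC.

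These figures assume 7 patients per physician, two physicians per site (one site with one physician at the minimum), and within-site correlations that the documents do not give. Monte Carlo error is about 0.1 to 0.2 percentage points.

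The claim of at least 0.8 power for the minimum sample does not survive a corrected site-level interval at ICC 0.3 (about 0.70), although at ICC 0.2 with no within-site correlation it just does (0.807). The method of point estimation is not in question. The pooled estimate draws on at least 4 × 10 = 40 sites; the step 2 formula gives coverage of about 0.94 there, so little change is expected.

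**What to change.** In section 5.2.1, carried over to 5.2.2, specify for the country intervals:
- site as the GEE cluster;
- a bias-corrected sandwich (Kauermann-Carroll or Mancl-DeRouen);
- a t quantile on the number of sites in that country minus 1 degrees of freedom;
- limits formed on the logit scale and back-transformed.

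Re-run Table 3 with this interval and with a stated range of within-site correlation. Then restate the minimum-sample power in section 5.1, and reconcile its independence assumption with the nesting promised in 5.2.1.

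The drafting cost is a paragraph and a re-run. Whether the software release used offers the correction directly should be checked; for an intercept-only model it can be computed from site totals.

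The real cost is wider country intervals (about 22% on the logit scale at 10 sites, 13% at 15) and lower stated power. At the minimum sample and ICC 0.3, Kauermann-Carroll with t gives about 0.70 with no within-site correlation and about 0.55 with an assumed within-site ICC of 0.15, against 0.804 stated. Mancl-DeRouen is more conservative and costs somewhat more power. The sponsor may then need to revisit the 10-site floor or accept the lower figure openly.
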